### **Clinic-based HIV/STI testing.**

At the end of the 12-month study period, all participants in all conditions will be asked to present to designated clinics for in-person HIV testing in exchange for a bonus payment (\$50). Encouraging participants in this way can help ensure that we have at least one accurate HIV test result for each (since some may elect not to test at all during the study period, regardless of condition). Results will allow us to more confidently estimate the number of new infections that were successfully detected or missed with HBST versus clinic-based testing reminders. For those who test positive, basic data from the sample (e.g., viral load, CD4 count at the time of confirmatory testing) will be collected from the medical records of each participant, provided they have signed a release. These data will permit us to estimate the "time since infection" for each participant diagnosed with HIV, allowing us to address our exploratory hypothesis that HBST could facilitate earlier diagnosis compared with encouraging clinic-based testing alone.

### **Clinic records.**

We will also review clinical data for each participant to compare with self-report data on HIV testing, STI testing, and PrEP uptake. We will obtain a signed HIPAA release to review the records of area clinics where participants reported receiving these services. Data on verified service use will be compared across conditions to explore potential differences. While we realize that this data may be incomplete (especially given that some may elect to test at certain sites anonymously), we believe that collecting as much corroborating data as possible will serve as an important compliment to self-report data. Data collected is limited to:

- Date of HIV test
- Viral load
- CD4 cell count
- Type of HIV test (blood vs. antibody)
- HIV status
- Whether the patient received counseling to reduce their risk for HIV
- Date of each STD test
- STD tested
- Test results
- Whether the patient spoke to a provider about PrEP
- Whether the patient was prescribed PrEP

\*Data Use Agreements will be put in place to allow staff at each study site access to the study database (saved on Brown's servers) in order to verify service use and enter data collected.

### **Individual interviews.**

RAs at each site will contact participants via phone at the end of the study to conduct a 30-minute individual interview about their experience using the eTEST app and HBSTs (if applicable). Interviews will inquire about the strengths/drawbacks of HBST versus clinic-based testing, their perceptions of the app and its features, and their preferences for follow-up/referral.

### **Procedure**

Ads will be placed with several MSM-oriented “hookup” apps (e.g., Grindr, Scruff, Jack’d) to recruit participants into the study. Ads will display to users who login to the apps within 30 miles of each metro. Clicking on the ad will direct users to a landing page for the eTEST study, where users can learn about the study and its requirements. A brief questionnaire will assess eligibility criteria, and those eligible will then be directed to register for the study, which will involve providing informed consent, basic personal information, and baseline questionnaire data (see Human Subjects for more details about online informed consent). The web app will then randomize participants to one of the three arms. Finally, for participants assigned to the enhanced condition, the web app will walk participants through downloading the eTEST app from the Google Play or iTunes stores. Access to the eTEST app will be restricted to users registered in the eTEST web portal who are directed specifically from that site. Participants will also be encouraged to keep the app downloaded on their phone throughout the study period and will be encouraged to register any changes in their mailing address or smartphone

information (number, phone OS) as soon as possible, either through the eTEST app, web portal, or by notifying study staff.

Once users have registered, staff will conduct a brief introductory call with all participants to ensure that their information is correct and that they understand the study's requirements. After successfully completing this call, study staff will mark these participants as 'fully enrolled,' activating them in the study database. For **control** group participants, test messages will be sent to remind users when they are due to test. Tests will include a link to a web service listing nearby clinics offering HIV testing, as well as their location, phone number, hours, and cost. For **standard** HBST group participants, staff will send an HBST kit to their confirmed shipping addresses. These participants will receive no phone-based follow-up, but can use OraSure's provided 1-800 number for questions or needs. We will follow the same steps for **eTEST** participants, except that each test kit will be fit with an Estimote™ beacon. Beacons will automatically detect when each kit is opened and relay this information to a central study database, which triggers an email notification sent to counselors. Within 24 hours of opening the kit, an HIV test counselor will call **eTEST** participants to conduct post-test counseling and refer them to other needed services, including PrEP (see Section 3C.3.6.1.). HIV test counselors will be bachelor's-level staff who are certified as HIV test counselors and will have crisis intervention training. Clinical assessment and analysis of mental health will remain a responsibility of the licensed study clinician. At least one HIV test counselor will also be fluent in Spanish. Counselors will record data during each call in the study database. In each condition, participants will receive these interventions every three months over the course of the study period: at baseline, 3, 6, and 9 months.

Online surveys will use Qualtrics and will be hosted on Brown University servers. On each quarterly survey's due date, the study database will automatically send participants an email with language-specific instructions and links to the surveys. Participants will be asked to complete these within two days, and reminder emails will be sent every other day for seven days after the due date. If participants have not completed the survey within a week of their due date, site-specific RAs will contact participants by phone, text message, and email to encourage adherence. For all participants, those who fail to complete two consecutive quarterly assessments will be considered to have withdrawn from the study. After participants complete their final online survey, they will be asked to present to designated clinics for in-person HIV testing to finish the study. Site RAs will conduct follow-up calls with participants to ensure adherence to this procedure. Study payments will be issued via a reloadable debit card that will be mailed after participants are activated in the study. Participants will earn \$25 for the baseline survey and each of the five quarterly surveys they complete, with a \$50 bonus for completing all within a week of their assignment. They will also earn an additional \$50 for completing the in-person HIV test after the study is finished, for a possible total of \$250.

Focused information/counseling on PrEP. PrEP education and counseling will take place at each post-test phone call with participants in the **eTEST** condition. During the first call, HIV test counselors will provide a brief PrEP education session, covering indications for PrEP eligibility, a description of the medication used for PrEP, and an overview of common side effects and clinical follow-up (every three months). In our past work, we have employed an effective, five minute PrEP education session during in-person HIV testing that resulted in greater PrEP awareness among MSM131, and this will guide the education delivered during HIV test counselor phone contacts. Following the education content, participants will be asked whether they are interested in making an appointment with a medical provider for PrEP consultation.

Interested participants will be provided with contact information for the local clinical sites where PrEP is provided. During subsequent phone calls, HIV counselors will re-assess PrEP interest and provide additional information upon request. Those indicating interest in PrEP at a prior call will be asked whether they made an appointment, initiated PrEP, and have attended follow-up appointments, which will be corroborated by reviewing medical records.

**Design Considerations.** We designed this study to approximate (as closely as possible) what the eTEST program might look if it were implemented in real-world settings, while also balancing the need to collect thorough and valid data on the program's effects over time. Given this, these procedures balance being as "hands off" as possible with conducting follow-ups that allow us to understand the program's effects thoroughly and accurately. This guided our decisions to (1) allow participants to consent and enroll remotely (2) use online surveys and (3) offer phone counseling to eTEST participants who test both positive *and* negative. First, while our pilot study required an in-person meeting for participants to enroll, the proposed research enables participants to provide consent and enroll remotely, because we believe one of HBST's key strengths is its potential to reach high-risk MSM who do not otherwise engage with traditional, "brick-and-mortar" services. Thus, to reach these high-risk MSM, we believe it is important to allow them to test more regularly without the inconvenience and stigma of a face-to-face appointment. We realize that this may present difficulties in terms of ensuring that participants are valid. However, to address this issue, multiple entries from the same IP or device will be blocked, and participants must verify their email addresses when registering, as well as other contact information via a call with staff after enrollment. Second, we chose to assess key self-report outcomes using quarterly online surveys to minimize participant burden, to minimize conditioning effects, and to allow a more accurate and "hands off" view of each conditions' effects. Since requiring in-person visits could artificially inflate adherence to key outcomes (e.g., HIV testing), we opted to use less burdensome online surveys. Third, the most important benefit of using the eTEST system is likely its ability to efficiently link those who test preliminary positive via HBST with confirmatory testing and care. As such, we considered several potential ways of providing phone follow-up with only these high-priority users (e.g., asking users to submit images of their test). However, some authors have noted that another key limitation of HBST is the lack of follow-up and referral for other services (e.g., STI testing, PrEP) for those who test negative. We believe that arriving at best practices for *how* to offer post-test follow-up with HBST and *with whom* are key questions that are best addressed after its effects are first well understood among *all* participants. That is, we believe it is important to first understand whether offering follow-up in both of these scenarios confers an appreciable benefit beyond standard HBST. Finally, we also realize that requiring eligible participants to have a smartphone with a data plan or home wifi may exclude an important subset of MSM who may be at high risk for HIV, including those with financial difficulties or unstable housing. However, this criterion is consistent with our focus on MSM who use "hookup" apps. Of the 1,269 participants screened from Grindr for the pilot study, 97% reported having a smartphone with a data plan. Recent data also shows that 60-80% of unstably housed individuals, including minority youth, had smartphones with data plans. Nevertheless, this requirement is a limitation of this study. Future work should

address this limitation by exploring other ways of providing monitoring/ follow-up after HBST, such as text messaging or by providing low-cost devices to users.

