#### **B.4 Design and Methods**

In the study phase, 2000 high-risk MSM who have not tested in the last year will be recruited from three metro areas, Providence/Boston, Jackson, MS, and Los Angeles, CA, using ads on MSM-oriented, geolocation-based mobile “hookup” apps. They will be randomized to receive one of the following at three month intervals over the course of a year: (1) HBST with remote monitoring and post-test phone counseling/referral (eTEST condition), (2) standard HBST without active follow-up, or (3) reminders to get tested for HIV at a local clinic, delivered via text messages (control condition). We chose a three month retesting interval (HBST/reminder) to align with the CDCs most stringent recommendations for high-risk MSM98. During the study period, participants will complete quarterly surveys online. At 12 months, participants will be asked to present to a local clinic to provide a blood sample for HIV testing, to facilitate exploratory analyses comparing the number of infections successfully detected in each group and the “time to diagnosis” in each condition (see 3C.3.5.2 for more detail).

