## Planned Analyses

Analyses will be conducted in Year 5. To evaluate Aim 1(a), we will use factorial logistic regression to test whether rates of having completed any HIV test over the 12 month study period (assessed via self-report and/or clinic records) differ by study condition. Condition, study site (and their interaction) and other relevant covariates will be entered as predictors, allowing us to explore whether each condition's effects differ by study site. To explore the effects of study condition on regular HIV testing, we will use a generalized estimating equation (GEE) for repeated, binary outcomes, specifying whether participants tested during each 3-month study period as the focal outcome. A logit link function and independent correlation structure will be specified, with study condition, site, and relevant covariates as predictors, to test whether the odds of testing differ across time period, condition, and site. GEEs are a fitting approach for studies in which correlations between repeated measures variables are to be controlled, rather than a central focus of the analysis. For all models of **HIV testing** outcomes, a covariate reflecting whether a given participant had initiated PrEP (and when, for longitudinal models) will be added to each model, since these individuals are required to test for HIV quarterly as a part of ongoing PrEP care. Doing so will allow us to estimate the effects of study arm on HIV testing among those who did not initiate PrEP. Given that we have proposed collecting 54 more participants per site (162 total) than is required to estimate our most complex model (see Model 1b in Section 3C.3.10), we believe we will be fully powered to test this model, even with a high rate of PrEP adoption. While contamination of the control group in our pilot study was rare (only one control participant reported using a HBST), we will also track **where** each participant tested (at home, in person) in quarterly surveys. If contamination is significant, we will employ methods aimed at reducing this bias, including adding indicators of contamination as covariates or bootstrapping. To evaluate Aim 1(b), we will generate variables reflecting whether participants received testing for other STIs or risk reduction counseling during each of the four 3-month intervals of the study period. Similar GEE models will be estimated for these outcomes with time period, condition, and site as predictors, to test whether the odds of receiving each service differ across these factors. To evaluate Aim 2, we will code variables indicating whether participant reports or clinic records reflect participants having consulted with a medical provider about PrEP and/or received a PrEP prescription any time across the study period. Factorial logistic regression with study site, condition, and their interaction will be entered as predictors of this outcome, to test whether the odds of having received consultation and/or a PrEP prescription differ across each of the study sites and conditions. Overall, data from those who drop out or withdraw from the study will be used in these analyses, in intent-to-treat (ITT) fashion. Similarly, we will assume values of zero for all outcomes (i.e., non-receipt of testing or services) when quarterly assessments are missing but participants are retained in the study. Depending on the degree of missing assessments, we will use multiple imputation for these values, since data from missing assessments will likely be missing not at random.

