
Exploratory analyses on new HIV cases and time to diagnosis. A key advantage of achieving more frequent testing through HBST could be the ability to detect more new infections and do so earlier, ideally before disease advances and others are infected. Given this, as exploratory aims, we will also examine whether more new cases are detected, and detected earlier on, using HBST compared to relying on clinic-based testing alone. To facilitate this, all participants will be tested in-person at the conclusion of the study, to ensure that HIV test results are available for most participants, even if they elected not to test using the study interventions. Among those who did not test during the study period, new cases detected through the post-study test will suggest that the interventions likely “missed” these cases. The proportion of cases detected with study interventions versus those missed can then be compared across conditions. Confirmatory testing in those who receive a reactive test at any time during the study, together with post-study testing for all participants, will also allow us to use CD4 counts and viral loads from positive blood tests to explore differences in estimated time to diagnosis among those infected during the study period, using methods described in past studies. These aims are secondary, however, since we acknowledge that there may be insufficient numbers of those infected with HIV during the study period in each group to conduct fully-powered tests. However, based on estimates of the rate of new infections among those without an HIV diagnosis in each study site’s area, we estimate that at least 20 participants (6 per group) may

be diagnosed with HIV during the study period. This will allow some limited exploration of these aims.

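### Two consecutive missed surveys count as withdrawal, and the protocol does not say whether men withdrawn this way still get later surveys, record review or the 12-month HIV test

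*Combined protocol and SAP*

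**What the plan says.** The Procedure section of B.4 says of all participants that "those who fail to complete two consecutive quarterly assessments will be considered to have withdrawn from the study". The trigger is survey response alone; no request to leave is needed. The next sentence reads: "After participants complete their final online survey, they will be asked to present to designated clinics for in-person HIV testing to finish the study".

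Three other places describe the exit test without a survey condition:

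- B.4 Design and Methods, opening: "At 12 months, participants will be asked to present to a local clinic to provide a blood sample for HIV testing".
- Clinic-based HIV/STI testing: "all participants in all conditions will be asked to present to designated clinics for in-person HIV testing". The reason given is to secure a result "since some may elect not to test at all during the study period, regardless of condition".
- Exploratory analyses on new HIV cases: "all participants will be tested in-person at the conclusion of the study, to ensure that HIV test results are available for most participants".

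Planned Analyses says that "data from those who drop out or withdraw from the study will be used in these analyses" on an intent-to-treat basis. It sets outcomes to zero "when quarterly assessments are missing but participants are retained in the study", with multiple imputation as an option depending on how much is missing. No rule is given for outcomes after a withdrawal.

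**The concern.** Missing questionnaires and leaving a trial are different events. The Procedure text merges them, and the protocol never says what follows for a man classed as withdrawn. If staff apply the two sentences as written, he gets no further surveys and never reaches the point at which the exit test is requested.

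Two things are then at stake. The first is self-report for Aims 1 and 2. Quarterly surveys ask about HIV testing since the previous assessment and services since the previous survey, so a man who returns after a gap could fill much of it. Planned Analyses itself expects missing assessments to be missing not at random, which makes avoidable loss costly. The second is the exploratory comparison of infections detected and missed. The exit test exists to give a result for men who did not test, and men who stop answering surveys may well be among them.

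**Working it through.** The protocol states no expected withdrawal rate, so there is no planned figure to reproduce. The check has two parts.

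**The texts side by side.** Procedure ties the exit test to completing the final survey; the other three sections tie it to the end of the 12 months and to all participants. The two agree for a man who completes the last survey. They disagree for a man withdrawn under the rule, and also for a man who misses only the last survey. Neither text addresses these men.

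**Size of the group.** Inputs:

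- Five quarterly surveys (Procedure; the payment total agrees: 6 × $25 + $50 + $50 = $250).
- 2000 men (B.4).
- 94% completion, the pilot's average for monthly surveys (B.1).
- 85% and 80% completion, which are assumptions, as is independence of misses.

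Let q be the chance of missing a survey and p = 1 − q.

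1. P(rule triggered) = 1 − (p⁵ + 5qp⁴ + 6q²p³ + q³p²). For q = 0.20: 1 − (0.32768 + 0.40960 + 0.12288 + 0.00512) = 0.1347.
2. P(first triggered at surveys 4 and 5, so no later survey to lose) = q²p(1 − q²). For q = 0.20: 0.04 × 0.80 × 0.96 = 0.0307.
3. P(at least one later survey lost) = step 1 minus step 2.
4. P(exit-test request never reached under the literal Procedure wording) = 1 − p(p⁴ + 4qp³ + 3q²p²). This adds men who miss the final survey. For q = 0.20: 1 − 0.80 × 0.896 = 0.2832.

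| Completion | Rule triggered | of 2000 | First at surveys 4–5 | Later survey lost | of 2000 | Request not reached | of 2000 |
|---|---|---|---|---|---|---|---|
| 94% (pilot) | 0.0137 | 27 | 0.0034 | 0.0104 | 21 | 0.0697 | 139 |
| 85% (assumed) | 0.0794 | 159 | 0.0187 | 0.0608 | 122 | 0.2016 | 403 |
| 80% (assumed) | 0.1347 | 269 | 0.0307 | 0.1040 | 208 | 0.2832 | 566 |

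Step 2 is 25%, 24% and 23% of step 1, or about a quarter.

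5. The exploratory section expects at least 20 diagnoses. At equal infection risk, men who trigger the rule would hold 20 × 0.0137 = 0.3, 20 × 0.0794 = 1.6 or 20 × 0.1347 = 2.7 of them. Not all would be lost, since some would be diagnosed before withdrawal or by another route.

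In practice misses cluster within people. At a given completion rate that raises the number who trigger the rule, but it also makes a later reply from them less likely.

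**The case against.** The strongest reply is that the protocol does not exclude anyone from the exit test. Procedure says when the request is made, and three sections say it goes to everyone. That is correct. A reader might infer that withdrawn men are barred from the test; the text is inconsistent or silent on them and goes no further.

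A reader might also infer that kits and reminders stop at withdrawal. No section says so, and Procedure describes the interventions as given at baseline and months 3, 6 and 9 in each condition.

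Nor is it right that the intent-to-treat analysis would have nothing later to use. Any HIV test may be counted from self-report or clinic records, and the study database holds kit openings and counselling-call data. These are partial substitutes. Releases are optional, and clinics are identified through the quarterly surveys (B.5.1.4). Kit openings and post-test calls exist in the eTEST arm only, and Planned Analyses does not list them as an outcome source.

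The protocol also works to prevent non-response: reminder emails every other day for a week, then contact by phone, text and email, with payment per survey and a bonus for timely completion. A man who triggers the rule has missed two surveys despite this, so recovery will be incomplete. It is further limited for Aim 2, because the PrEP consultation item covers only the last month. A later survey can record later consultations but cannot fill the gap.

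Finally, the exit test serves exploratory aims with few expected cases. That limits the consequence without removing the inconsistency.

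**Conclusion.** The point holds as an inconsistency and an omission that are cheap to repair. Survey non-response is made equivalent to withdrawal, the exit-test request is described in two incompatible ways, and follow-up after such a withdrawal is undefined. Followed literally, the Procedure text gives up self-report that could have been recovered for Aims 1 and 2, and weakens the exploratory detected-versus-missed comparison. The intent-to-treat and zero-value rules do not restore data that were never collected.

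The size is modest at the one documented completion rate: 1.4%, about 27 of 2000. It reaches 7.9% to 13.5% (about 159 to 269) only if completion falls to 85% or 80%, which is assumed. These figures rest on five surveys and independent misses. The 94% comes from a 73-man pilot that was shorter and enrolled in person.

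Two further inferences are tempting and not documented. One is that withdrawal would differ between arms, which is plausible because contact differs, but no figure supports it. The other is that the pilot's 8% loss (92% retained) measures this rule; nothing links that loss to missed surveys.

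**What to change.** Amend the Procedure section of B.4 to say that survey non-response alone is not withdrawal, and bring its exit-test sentence into line with the other three sections:

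- Keep sending the remaining automated surveys to men who have missed earlier ones.
- Continue clinic-record review wherever a release exists.
- Invite every randomised participant who has not withdrawn consent to the 12-month HIV test, whether or not the final survey was completed.
- State in Planned Analyses how outcomes are handled after a true withdrawal.

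The protocol should also say whether kits and reminders continue for men who stop answering surveys. The sponsor needs to reconcile the sections on this; B.5 raises secure delivery as a consideration, and this review does not propose an answer.

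The cost is a wording change, a change to how the study database flags withdrawal, some extra research-assistant contact, and additional payments of $25 per survey and $50 per exit test for men who respond.
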